AKI, defined as a sudden decrease in function and damage to kidneys is common among critically ill patients. The creatinine based Kidney Disease Improving Global Outcomes (KDIGO) criteria define AKI as an increase in serum creatinine by 1.5 times the baseline creatinine of by $\geq 0.3\text{mg/dL}$ [2]. The incidence of AKI at 2.1 per 1000 population is similar to that of heart attacks [3]. It is seen in 10-15% of all hospitalized patients but has been described in over 50% of critically ill patients [4, 5]. It has been described to be present among 15-25% patients with COVID-19 [6, 7].

AKI is not only common but is associated with 3-4 times higher mortality [8, 9], development of chronic kidney disease [10], end stage renal disease [11] and increase in healthcare expenditure [12]. There are no definitive therapies for AKI and treatment primarily rests on prevention of progression of AKI and management of its complications such as hyperkalemia, acidosis and volume overload. Approximately 6-13% of critically ill patients develop severe AKI that requires life-saving dialysis therapy [5, 13] but dialysis itself is associated with high mortality [13] and life-threatening complications such as infections. Therefore there is a great interest in developing therapies and treatment approaches that can prevent AKI in critically ill patients.

2. Hypothesis

We hypothesize that alkalization of urine is safe and effective to prevent development of AKI in patients with COVID-19

3. Significance

Although COVID-19 primarily affects the lungs and may cause severe hypoxemia, other organs including the GI tract, heart and kidney are affected. Acute kidney injury secondary to COVID-19 (COV-AKI) is reported to occur in about 15-25% of patients hospitalized with COVID-19 infection. [6, 7] However, AKI was much more common in non-survivors ($>50\%$). The majority of AKI cases are mild to moderate with renal replacement requirement in about 25% of AKI cases. But with COVID-19 taking the form of a pandemic, this has translated into thousands of patients needing dialysis. There are already reports of hospitals running out of dialysis machines to provide life-saving therapy critical for COVID-19 patients with AKI. As such there is a critical need to identify therapies that can delay the development or progression of AKI in these patients. Although kidney failure appears to occur late in the course, patients may begin to

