Thus, the innovative idea of simply drinking sodium bicarbonate solutions to induce minor changes in blood pH has been proposed.[21] This idea suffers from two major limitations. First, the pH change required to have significant effect on disrupting the RBD is likely to be too great to safely achieve in blood—a rule of thumb is at least 1 pH unit.[23] Second, even if this could be achieved the expression of ACEr is on the apical (lumen) surface of epithelial cells not the basolateral (plasma) side.[16] However, neither of these are problems for the kidney. Urine pH

is normally 5.5-6.5 (not too dissimilar to alveolar fluid—6.4-6.8[24]) and can be easily and safely manipulated. In fact, urine alkalinization protocols have been used for decades to reduce renal toxicity from various compounds (especially chemotherapy) and are recommended by US and European toxicology societies.[25] Here, the strategy will be deployed not for ion trapping but to inhibit the virus from infecting RTEC. Alkalizing the urine using IV sodium-bicarbonate solution to pH of 7.5 or more can be easily and safely achieved. Acetazolamide can also be added if systemic alkalemia is an issue.[25] An additional advantage of this approach is that it is unlikely to interfere with other interventions that can be studied in these patients (e.g. steroids) which are directed at the lungs.

5. Approach

We will conduct a pragmatic RCT using alkalinization of urine such that most ICU COVID-19 positive patients can be enrolled. Both specific aims will be achieved by the conduct of the trial yet both are independent. The statistical analysis plan for each aim will detail the specific endpoints and hypotheses being testing.

Trial overview: Study inclusion and exclusion criteria are provided in Table 1.

Study design: Open-label randomized trial (1:1) comparing urine alkalinization to standard care. The study will test both feasibility and safety (aim 1) as well as efficacy (aim 2).

Study Management: Study personnel will identify patients and obtain video-enabled informed consent from patients or legally authorized representatives; collect study data and ensure sample collection, processing and storage. The patient's bedside nurse will perform urine pH measurement (dipstick) and deliver the study drug. The study is open-label to facilitate safety and allow for any management of complications (e.g. calcium supplementation).

Table 1. Inclusion/exclusion Criteria

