Primary feasibility outcome will be the proportion of patients treated who achieve >50% of urine measurements pH \geq 7.2 over the duration of treatment. Following specific adverse events will be monitored – hypokalemia (K<3.0meq/L), hypocalcemia (Ca<7.6mg/dL when corrected for albumin), Hypernatremia (Na>155meq/L), Volume overload (gaining weight >10% from admission weight during the protocol time-period, need for positive pressure ventilation or intubation due to volume overload), arrhythmias due to hypokalemia or hypocalcemia. To assess safety and feasibility, summary statistics including frequency, mean, standard deviation, median and interquartile range will be provided as applicable. Baseline data will be summarized comparing treatment groups over time. Chi-square/t-test will be used to compare the difference between treatment groups. Mixed model /ANCOVA will be used for repeated measurements over time.

As per the requirements of COE, a Data Safety Monitoring Board (DSMB) has been established that includes [name] [name], [name], [name] and [name] [name]. The DSMB will meet to review any adverse events after 5 and 25 patients have been recruited. In addition, as per the requirements of COE, the DSMB will meet to review any adverse events after the first 5 patients randomized to the interventional drug (open label arm) have been recruited and completed the study.

Aim 2: To determine the efficacy of urine alkalinization for prevention of AKI

Primary efficacy outcome will be the number of days alive and free of stage 2-3 AKI (up to 28) in each group. Secondary endpoints will include the proportion of patients developing stage 2-3 AKI (or stage 3 if already at stage 2 at enrollment); ventilator-free days to 28 and hospital-free days to 60. For AKI-free, ventilator-free, and hospital-free days, zero truncated negative binomial models will be implemented.

Severe AKI will be considered as binary outcome. Multivariable logistic regression will be used to assess the overall odds associated with treatment adjusted by baseline covariates (age, demographics, baseline renal function). Random forest decision tree regression method will be implemented to assess patient variable importance towards the outcome. Hazard will be assessed using cox proportional hazard model.

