Sample size determination: The study will be powered to achieve a 50% increase in the number of days alive and free of stage 2-3 AKI to day 28. We hypothesis an increase from 10 +/- 5 days to 15 +/- 5 days. The sample size needed to achieve this difference is 16 patients per group. We plan to enroll 20 patients per group for a total sample size of 40 patients. [name], Professor of Critical Care Medicine at the University of Pittsburgh and a co-investigator on this application is working towards a similar trial at the University of Pittsburgh (see attached letter of

support). The results from both these studies will then be pooled and changes in AKI rates, and survival will be examined.

Relevance to the current COVID-19 pandemic

There are at least four reasons why this study will have an important impact. First, when severe AKI does occur, mortality is very high.[6, 7] Preventing early AKI may reduce severe AKI as the disease progresses. Second, AKI has considerable effects on the immune system reducing a variety of immune functions[28] and hence might contribute to reduced host response. Third, this is unlikely to be the last β-coronavirus outbreak and different strains may cause even more AKI. Finally, the results of this study would provide critical proof of concept data that could be used to design other therapies to reduce viral RBD affinity. For example, alveolar pH could also be manipulated. Showing feasibility with this safe and available strategy could be the first step toward other related efforts.

C. REFERENCES

2. **KDIGO Clinical Practice Guideline for Acute Kidney Injury** [<https://kdigo.org/wp-content/uploads/2016/10/KDIGO-2012-AKI-Guideline-English.pdf>]

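### Aim 1 is to determine safety, but no planned output states how much excess harm the data exclude; report adverse events with confidence intervals and do not rest on a test for a difference

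*Combined protocol and SAP*

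**What the plan says.** All references are to the combined protocol and SAP, part B (Research Strategy).

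- Section 2, Hypothesis: "We hypothesize that alkalization of urine is safe and effective to prevent development of AKI in patients with COVID-19". Aim 1 is to determine feasibility and safety.
- Section 5, Statistical analysis, Aim 1, on events: "Following specific adverse events will be monitored". The list is hypokalemia, hypocalcemia, hypernatremia, volume overload and related arrhythmias. Each is defined so that a patient either has it or does not.
- Same paragraph, on method: "To assess safety and feasibility, summary statistics including frequency, mean, standard deviation, median and interquartile range will be provided as applicable". A sentence on summarizing baseline data by group follows, and then "Chi-square/t-test will be used to compare the difference between treatment groups". The paragraph closes by assigning a mixed model or ANCOVA to repeated measurements.
- Section 5, Study design: "Open-label randomized trial (1:1) comparing urine alkalinization to standard care".
- Section 5, Sample size determination: "We plan to enroll 20 patients per group for a total sample size of 40 patients". The calculation concerns AKI-free days only.

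The documents give no confidence interval, safety margin, expected adverse-event rate, significance level or power for safety.

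**The concern.** A chi-square test takes no difference as its null hypothesis. With 20 patients per arm, failing to reject that null is weak evidence, because a large excess can easily go undetected. A safety aim asks how much extra harm is still compatible with the data. Frequencies and a p-value do not answer that directly; an interval does.

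At stake is the sentence in the final report that answers Aim 1. If the arms do not differ significantly on, say, hypernatremia, the plan supplies neither a figure nor a rule to stop a reader from taking this as support for the hypothesis that alkalinization is safe. The section on relevance already presents the strategy as safe and as a possible first step toward related work, so the safety statement is likely to be carried forward.

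**Working it through.** **Inputs from the documents.** 1:1 allocation; 20 per group; binary adverse events; chi-square for group differences. The plan has no imputation and no allowance for dropout, so 20 analysed per arm is the best case.

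**Assumptions.** The significance level is not stated; I take two-sided 0.05 and then vary it. Control event rates are not stated; I use 0% to 20%. The 20-point excess is illustrative. The plan does not say whether chi-square is corrected or replaced by an exact test, so I show uncorrected chi-square and Fisher.

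**1. The plan's own figure.** The plan says "We hypothesis an increase from 10 +/- 5 days to 15 +/- 5 days" and "The sample size needed to achieve this difference is 16 patients per group". With two-sided 0.05 and 80% power (both assumed), n = 2(1.96 + 0.84)² × 5² / 5² = 15.7, which rounds up to 16. The figure reproduces, but it says nothing about safety.

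**2. Probability of missing a true 20-point excess.** Sum the product of the two binomial probabilities over all 21 × 21 possible tables, counting those where the test is not significant.

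| Control v treated | Missed, chi-square | Missed, Fisher |
|---|---|---|
| 0% v 20% | 41% | 63% |
| 2% v 22% | 48% | 66% |
| 5% v 25% | 56% | 70% |
| 10% v 30% | 64% | 76% |
| 20% v 40% | 71% | 81% |

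The first row can be checked by hand. With no control events, chi-square needs at least 4 treated events and Fisher at least 5. For a binomial with n = 20 and risk 0.2, P(4 or more) = 0.589 and P(5 or more) = 0.370. The misses are therefore 1 − 0.589 = 41% and 1 − 0.370 = 63%.

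For uncorrected chi-square, power crosses one half at a control rate just under 3% (0.509 at 2.5%, 0.495 at 3%).

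**3. Varying the significance level.** With two-sided 0.10, uncorrected chi-square misses the excess in 41% (5% v 25%), 51% (10% v 30%) and 59% (20% v 40%).

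**4. What an interval would show.**

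- Per-arm risk, Clopper-Pearson. For 0/20 the upper 95% limit is 1 − 0.025^(1/20) = 16.8%. For 1/20 it is 24.9%, and for 2/20 it is 31.7%.
- Risk difference, Newcombe, equal counts. For 0 v 0, the Wilson upper limit in each arm is 3.84/(20 + 3.84) = 16.1%, so the difference interval is −16 to +16 points. For 1 v 1 it is −19 to +19, and for 2 v 2 it is −21 to +21. Exact unconditional intervals are slightly wider, at ±18, ±20 and ±23.
- An unequal example: 4/20 treated v 1/20 control. The pooled risk is 5/40 = 0.125, so chi-square = 0.15² / (0.125 × 0.875 × 2/20) = 2.06 and p = 0.15. The Newcombe interval is −7 to +37 points. The p-value alone hides that upper limit.

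**The case against.** **The test may not be meant for adverse events.** The sentence that names safety promises description, and the chi-square sentence comes straight after one on baseline data. This stands as a caution: applying the test to adverse events is the natural reading, not the only one. If it covers baseline data alone, however, the binary adverse events have no comparative method at all, and the need for intervals is greater.

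**The test is not the only comparative method.** The mixed model or ANCOVA could be applied to serial sodium, potassium and calcium values and would give estimates with standard errors. That is correct, so it would be wrong to say that the plan compares groups only by testing. But that method is assigned to repeated measurements. It does not give the risk of crossing a listed threshold, nor of volume overload or arrhythmia.

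**Nobody says that non-significance means safe.** A reader might infer that the plan will declare safety from a non-significant test. No section says so. The gap is the absence of any output or rule that would prevent that reading.

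**A large excess is not always missed more often than not.** A reader might infer that it is. The documents give no event rates, no significance level and no test version. With uncorrected chi-square and a control rate below about 3%, which is possible for the rarer events, the excess is found slightly more often than missed. With counts as low as 0 v 4, though, the expected events are 2 per arm, and an exact test would be the usual choice.

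**Readers can compute intervals themselves from the frequencies.** They can, so no information is lost. The trial's own conclusion would still be written without them.

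**This is a 40-patient feasibility study with a DSMB.** The DSMB reviews events at set enrolment points, so oversight during the trial does not hang on a final p-value. The plan gives the board no numerical criteria, and its reviews do not settle how the final report answers Aim 1. Small size is a reason to prefer estimation to testing.

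**Conclusion.** The concern holds in a limited form. The plan sets out to determine safety, but for its binary adverse events it provides frequencies and, on the natural reading, a test for a difference. No planned output states the excess harm that the data rule out.

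At two-sided 0.05 with 20 analysed per arm, a 20-point excess is missed in 56% to 71% of trials by uncorrected chi-square and in 70% to 81% by Fisher, for control rates of 5% to 20%. At 0% v 20% the figures are 41% and 63%. Even equal counts of 0 to 2 events per arm leave about 16 to 21 points not excluded. The power figures rest on assumed event rates, an assumed significance level and an illustrative excess; the interval limits depend only on the counts, the 20 per arm and the 95% level.

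This is a reporting weakness worth correcting. It is not evidence that the intervention is unsafe, nor that the sponsor intends to equate non-significance with safety.

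**What to change.** In the Aim 1 paragraph of the statistical analysis:

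1. For each listed adverse event, make the safety result the number and risk per arm with a Clopper-Pearson 95% interval, and the risk difference with a Newcombe or Miettinen-Nurminen 95% interval. Name the chosen method; neither of the last two is exact.
2. Say whether the chi-square/t-test sentence applies to adverse events. If it does, call those p-values descriptive.
3. State that a non-significant difference will not be reported as showing safety, and that the conclusion will quote the largest excess risk not excluded.

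The cost is a few sentences and a few lines of code, using data already to be collected; enrolment and patient care are unchanged. The downside is a more cautious safety statement. The change discloses the limit set by the sample size and does not remove it: by the normal approximation, 80% power for a 20-point excess would need 49 per arm (5% v 25%), 62 (10% v 30%) or 82 (20% v 40%).

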develop AKI within the first 3 days of hospitalization.[6] Thus, there may be a long window for treatment and prevention of early AKI that may decrease renal failure.

Similar to AKI in other settings,[14] COV-AKI is likely to be of variable etiology. Most patients present with single-organ failure (severe hypoxemia). Thus, remote organ injury, including AKI can simply be a consequence of critical hypoxia. Late cardiac involvement, reported in some series, may also cause cardio-renal syndrome. Furthermore, while typical cases do not appear to cause significant hyperinflammation, a few patients develop a microphage-activation syndrome-like phenotype with cytokine storm and high plasma ferritin. This may be the cause of severe AKI in this subgroup. **However, AKI might also result from direct infection of renal tubule epithelial cells (RTEC).** A variety of epithelial cells express the ACE2 receptor and this receptor is used by β -coronaviruses to enter the cells.[15, 16] An autopsy study of 26 COVID-19 patients recently confirmed the invasion of RTECs by SARS-CoV2 with COVID-19[17].

It is this direct viral involvement of the RTEC that this proposal seeks to address. One relatively obvious solution would be to block the ACE2 receptor pharmacologically and hence prevent the virus from entering the cells. While this could be an attractive therapy, ACE2 activity has been shown to be protective in lung injury[18] and no renal specific ACE2r antagonists are available to study. An alternative approach would be to perturb the ability of the receptor-binding domain (RBD) of β -coronaviruses[15] to bind to its cellular (hACE2) receptor. Changes in pH[19] may cause each amino acid residue in the RBD to assume a slightly different 'microscopic' conformation-dependent pKa value. Conformational change may alter the affinity of the RBD for its receptor and this may not jeopardize the function of the enzyme. The pH-induced potential for minor conformational change and/or steric hindrance[20] is possible due to the bulky phenylalanine residue in position 486 (F486 in h2019-nCoV RBD6) and in positions 442 and 472 (Figure 1).[21]

[figure not shown]

Figure 1. Structure of hACE2 receptor and the SARS-CoV RBD.[22]

4. Innovation

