Inclusion Criteria	Exclusion Criteria
Confirmed COVID-19 +	Stage 3 AKI by KDIGO criteria
Admission to ICU or step-down units at WVU	CKD stage 4-5
Foley catheter* and central line (or PICC) in place	Contraindications to Na bicarbonate therapy (e.g. met. alkalosis, severe heart failure)
Age ≥ 18 y	Urine pH > 7.0
	ECMO Patients

*Foley Catheter can be removed 72 hours after enrollment if appropriate documentation of urine output can be maintained

Urine alkalinization may also increase the elimination of certain drugs including hydroxychloroquine. We do not intend to exclude patients taking these drugs but it will be discussed in the consent form and with the treating physicians.

Intervention: The intervention is a modification/simplification of a standard protocol used for decades for the treatment of various drug toxicities (e.g. salicylate) or to mitigate kidney damage from chemotherapy.[25] Simplifications are intended to tailor the intervention to the management of COVID-19 patients and reduce or eliminate any additional staff exposure. We will continue urine alkalinization for 10 days or until patient is discharged from ICU or step-down unit or until the stage 3 AKI or a safety endpoint is reached. Urine pH will be measured at POC by dipstick. The major elements of the interventional protocol are shown in Table 2. Note, much of the monitoring (e.g. blood gases, calcium) is already performed for routine care. The protocol simply ensures that these measurements are timed to maximize patient safety and minimize burden on bedside nurses. The protocol has been developed with input from [name], Professor and Vice Chair for Research in the Department of Critical Care Medicine at the University of Pittsburgh.

Table 2. Protocol highlights
Sodium bicarbonate 225 mmol (225 mL of an 8.4% solution) intravenously over 1h
Recheck urine pH (dipstick) in 2-4 hours (from start of infusion)
Repeat boluses of intravenous sodium bicarbonate to achieve urine pH ≥ 7.2
Monitor urine pH every 2-4 hours until target is reached and then q6-8 hours
Sodium bicarbonate 8.4% solution should not exceed 900 ml (4 boluses) in 24h
Monitor plasma sodium, potassium, calcium every 12 hours and Acid-base status at least every 24 hours (Note: Arterial pH should not be > 7.50 , or venous > 7.55)
Acetazolamide (Diamox) can be administered at physicians' discretion to control systemic alkalinization and to help avoid fluid accumulation.

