Avoid fluid accumulation. If urine output does not increase to compensate for the increased fluid (it will in most cases, especially if kidney is protected), Lasix or Diamox can be added.
*If fluid balance cannot be maintained within +1L in 24 hours – protocol will be halted and resumed only if either the fluid balance can be correct to within +500mL in 24 hours or if the primary team decides that the patient has clinically appropriate fluid balance.

Data

collection: Information will be collected about patient demographics – date of birth, age, sex, race, weight, height, co-morbidities including but not limited to diabetes, hypertension, heart failure, coronary artery disease, previous cardiac surgeries, chronic kidney disease, cancers. Given the long history and familiarity with urine alkalinization, potential adverse effects (e.g. metabolic alkalosis, hypocalcemia) are well known. Data about renal function (creatinine, urine output, daily ins and outs), basic metabolic panel, blood gas, home medications, medications given during hospital stay and chart review to identify any relevant complications will also be performed. The provider survey will be performed using an online survey instrument and a link will be emailed to the provider to complete.

Sample collection: We will collect urine samples (1 before, 1 at 24 hours and 1 at 48 hours) from initiation of the protocol. Urine samples will be collected, processed and stored in accordance

with EH&S requirements for COVID-19 samples. At a later date and using alternative funding, we plan to analyze these samples for additional biomarkers either at WVU or at partner institution(s) in that study.[26] These biomarkers measure the cellular stress in the kidney[27] and will be examined in an ancillary study. The samples will be stored initially at the laboratories in WVU and then shipped to partner institution(s) for further testing of urine biomarkers as detailed above.

Statistical analysis: Descriptive statistics will be used for reporting: continuous variables expressed as median and interquartile range while categorical variables as frequency and percentages. No imputation will be performed and missing data will be treated as missing.

Aim 1: To determine feasibility and safety of a pragmatic urine alkalinization protocol for the prevention of AKI

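### Patients can enter at stage 2 AKI, but entry stage is neither a stratification factor nor a named covariate in the primary days analysis: a modest precision gain is left unused

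*Combined protocol and SAP*

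**What the plan says.** - **Eligibility (Table 1).** The only exclusion for current AKI is "Stage 3 AKI by KDIGO criteria". Patients with no AKI, stage 1 or stage 2 may enrol. Section 5, Approach, wants the trial to be run "such that most ICU COVID-19 positive patients can be enrolled".
- **Timing of AKI (3. Significance).** Patients may begin to "develop AKI within the first 3 days of hospitalization". The same sentence opens by saying that kidney failure tends to come late.
- **Design (Study design).** "Open-label randomized trial (1:1) comparing urine alkalinization to standard care". No stratification factor is named.
- **Endpoints (Statistical analysis, Aim 2).** The primary outcome is days alive without stage 2-3 AKI, up to 28. A secondary endpoint is "the proportion of patients developing stage 2-3 AKI (or stage 3 if already at stage 2 at enrollment". That allowance for stage 2 at entry is not made for the primary outcome.
- **Models (Aim 2).** "For AKI-free, ventilator-free, and hospital-free days, zero truncated negative binomial models will be implemented". No covariate is attached. The only Aim 2 covariate list (age, demographic factors, renal function at baseline) belongs to the logistic model for severe AKI. The ANCOVA mentioned under Aim 1 is for repeated measurements.
- **Sample size determination.** "We hypothesis an increase from 10 +/- 5 days to 15 +/- 5 days", giving 16 per group, with 20 per group planned.
- **Data collection.** "Data about renal function (creatinine, urine output, daily ins and outs" are already recorded.

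**The concern.** A patient at stage 2 on day 0 is already losing days on the primary outcome, so entry stage is tied to that outcome by construction. The plan recognises such patients when it defines the secondary proportion, but uses entry stage in neither the allocation nor the primary analysis. With 20 patients per arm, the split of stage 2 patients is left to chance. An uneven split adds noise to the estimate and can mask or exaggerate a treatment effect in this trial's own result. A covariate named in advance recovers that precision from data already in hand. One chosen after results are seen, in an open-label trial, would be open to challenge.

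**Working it through.** **1. The plan's own figure.** Difference 5 days, SD 5. Alpha, sidedness and power are not stated; two-sided 5% and 80% are assumed because they reproduce the result: n = 2 × (1.960 + 0.842)² × (5/5)² = 15.7, so 16 per group. At 20 per group, two-sample t-test power is 86.9%.

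**2. Assumptions.** Let p be the share entering at stage 2 and D the number of days such a patient loses, the same in both arms. The documents give neither. The COVID-19 rate of 15-25% in the background sections is any-stage AKI, not stage 2 at entry. I use p = 5%, 10%, 20% and D = 2, 5, 8.

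**3. Chance imbalance.** The difference between two Binomial(20, p) counts gives:

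| p | Arms differ by 3 or more | By 4 or more |
|---|---|---|
| 5% | 6.7% | 1.3% |
| 10% | 18.0% | 6.3% |
| 20% | 32.0% | 16.4% |

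A 4-patient difference moves the unadjusted estimate by 4/20 × D: 1.0 day at D = 5 and 1.6 days at D = 8, against a planned 5.

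**4. Power with entry stage in a linear model.** R² = p(1−p)D²/25; adjusted SD = 5√(1−R²); noncentral t with 37 df, 20 per arm. The unadjusted figure is 86.9% throughout.

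| p | D = 2 | D = 5 | D = 8 |
|---|---|---|---|
| 5% | 87.1% | 88.4% | 90.7% |
| 10% | 87.3% | 89.8% | 93.9% |
| 20% | 87.7% | 91.9% | 98.0% |

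Example: p = 10%, D = 5 gives R² = 0.1 × 0.9 × 25/25 = 0.09 and SD = 4.77. The formula ignores the small loss when stage is unevenly split, so it is slightly optimistic. If stage has no prognostic value, the formula shows a loss of about 0.1 point, and a linear simulation about 1 point.

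**5. Power under count models.** Simulated days were rounded normal values clipped to 0-28, with control mean 10, total SD 5, treated arm +5, and 2,000 trials per setting. The planned zero-truncated negative binomial model gave, without and with entry stage:

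| p, D | Without | With | Gain (points) |
|---|---|---|---|
| 5%, 5 | 83.6% | 85.5% | 1.9 |
| 5%, 8 | 85.2% | 88.3% | 3.1 |
| 10%, 5 | 84.7% | 87.4% | 2.7 |
| 20%, 5 | 83.0% | 88.8% | 5.8 |
| 10%, 8 | 82.9% | 92.1% | 9.2 |
| 20%, 8 | 83.0% | 97.4% | 14.4 |

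An ordinary negative binomial model, which keeps zeros, gave 84-86% without and 88-98% with at the four 10-20% settings. Under no effect, the truncated model rejected in 5.0-6.6% of trials without the term and 5.4-6.7% with it.

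**6. What truncation does to these patients.** In the same set-up, a stage 2 control patient has mean 10 + pD − D. The chance of scoring 0 is Φ((0.5 − mean)/adjusted SD); a treated patient has a mean 5 days higher.

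| p, D | Control mean, SD | P(0 days), control | P(0 days), treated |
|---|---|---|---|
| 10%, 5 | 5.5, 4.77 | 15% | 2% |
| 20%, 5 | 6.0, 4.58 | 11% | 1% |
| 10%, 8 | 2.8, 4.39 | 30% | 5% |
| 20%, 8 | 3.6, 3.84 | 21% | 2% |

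A zero-truncated model leaves these patients out, more often from the control arm when treatment works. An entry-stage term cannot bring them back.

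**7. Too few stage 2 patients.** Among 40 patients, none enters at stage 2 with probability 0.95⁴⁰ = 12.9% at p = 5% and 0.9⁴⁰ = 1.5% at p = 10%. Two or fewer enter with probability 68% and 22%.

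**The case against.** **The gain may be very small.** Prevalence and prognostic effect are both assumed, and the remark that kidney failure tends to come late points towards fewer stage 2 entrants. At 5% prevalence, or if stage costs only 2 days, the gain is 0-3 points or thereabouts. Power without the term is already 83-87% in every setting above. This stands, and it limits the weight of the point.

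**Randomisation already protects the comparison.** A reader might infer that the unstratified design biases the trial. The documents do not support that: allocation is random, and chance imbalance costs precision. The opposite blanket statement, that only precision is at issue, is also too strong. It holds for an analysis that keeps patients with 0 days, not for the zero-truncated model.

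**Unfavourable splits are selected cases.** At the four 10-20% settings, when the treated arm drew 3 or more extra stage 2 patients, simulated power was 48-70% without the term and 83-96% with it. Such trials are 9-16% of the total, and favourable splits are equally likely. The unconditional gains are the fair summary.

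**Results will be pooled with a second centre.** They will, so this is not the only evidence planned. But the pooling is described for AKI rates and survival, and does not rescue this trial's days analysis.

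**Renal function at baseline is already adjusted for.** Only in the logistic model, and the term is undefined.

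**Conclusion.** The gap is real: stage 2 patients are eligible and expected, and nothing in the allocation or the primary days analysis uses entry stage. In an analysis that retains zeros, the consequence is lost precision. Its size rests on assumed prevalence and days lost: about 0-3 points of power at about 5% prevalence or a 2-day effect, about 2-6 points at 10-20% and 5 days, and larger gains only near 8 days. This is a modest, cheap improvement.

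Three stronger readings should be resisted. The trial is not shown to be underpowered for want of this covariate. Adding it does not make the zero-truncated model sound, because the omission of patients with 0 days is a separate problem. Nor does the point require a smaller logistic model for severe AKI: that is a secondary analysis, and dropping its covariates is a debatable trade-off that belongs elsewhere.

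**What to change.** In Statistical analysis, Aim 2:

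1. Name baseline AKI stage (0-1 vs 2), derived from the creatinine and urine output already collected, as a covariate in the primary days analysis.
2. Fit it in a model that retains patients with 0 days, such as a linear model on the scale of the sample size calculation or an untruncated count model. State the effect measure and test in advance.
3. State that the term is dropped if fewer than a prespecified small number of stage 2 patients enrol, for example 3. A rule that acts only when none enrols is too thin, since with one such patient the term in effect removes that patient.

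The cost is SAP wording and one degree of freedom, with no new data or patients. The gain is small if few patients enter at stage 2. At 5% prevalence, the rule with a minimum of 3 would drop the term in 68% of trials.
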